5.8.2. Helminthiasis

Treatment for helminthiasis, with mebendazole or albendazole, will be provided free of charge by the Sponsor for use as per usual practice in the investigational centres.

Treatment for helminthiasis will be followed by a recovery period of at least 3 days between the last dose of the antimalarial agent and the first administration of treatment for HAT, as per usual practice in the investigational centres.

5.8.3. Contraception

For girls of child-bearing potential, i.e. \geq 12 years of age, the Investigator will first decide whether or not it is appropriate to discuss contraception with the patient, i.e. depending on whether or not she is sexually active. If so, the Investigator will recommend the use of a contraceptive method or abstinence during the treatment period and, if possible, until cure is confirmed. Medically proven methods of contraception, i.e. hormonal contraception and condoms, will be available to patients free of charge during the 18-month follow-up period.

5.8.4. Other Medication

Unless there is an urgent medical need, patients should refrain from using any medication required to treat concurrent conditions until after the end of the treatment of HAT.

Any medication used during the hospitalisation period must be recorded in the CRF, specifying the reason for use.

Information on any SAEs that may occur during the follow-up period will be collected at unscheduled visits and recorded in the eCRF, specifying any medication received. Other medical events will be recorded only in the patient's medical file.

Any essential medicine required during the study period, i.e. up to the 18-month follow-up visit, will be provided to the patient free of charge. The WHO List of Essential Medicines and the MSF reference guide entitled *Essential Medicines* (2010 edition) will be used as a basis for treatment of any concurrent condition. For any chronic condition, the study team will take all necessary measures to ensure that the patient is referred to the most appropriate healthcare facility in the region.

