2.2.2. Secondary Endpoints

Efficacy

Result (success or failure) at each visit from the end of treatment to month 18.

Safety Endpoints

Adverse events (AEs) will be graded according to the Common Toxicity Criteria for Adverse Events (CTCAE) of the National Cancer Institute (NCI), Version 4.03.

- Occurrence of any AEs grade ≥ 3, including laboratory abnormalities, during the observation period;
- Occurrence of any AEs, at any grade, during the observation period;
- Occurrence of any treatment-related AEs (grade ≥ 3 and any grade) during the observation period;
- Occurrence of any SAEs between the first intake of the IP and the end of the follow-up period (18 months).

ECG abnormalities with no clinical symptoms will not be reported as AEs. ECG changes will be analysed separately. If cardiac symptoms are present, information collected from ECG will be recorded in the eCRF.

PK Endpoints

Concentrations of fexinidazole, M1 and M2 in whole blood and CSF, and PK parameters derived from a population PK model.

 Samples of whole blood will be collected using dry blood spot (DBS) testing on venous puncture at the following timepoints:

- On Day 10, 3 hours and 7 hours 15 minutes after the last intake of fexinidazole;
- o On Day 11, i.e. 24 hours after the last intake of fexinidazole;
- o On Day 12, i.e. 48 hours after the last intake of fexinidazole.
- Lumbar puncture will be performed at Day 11, 24 hours after intake of fexinidazole for the EOT efficacy assessment in the first 30 patients. A dry CSF spot will be collected at the same time for PK analyses in the first 30 patients.

ECG Endpoints

Triplicate ECG tracings will be recorded at 2-minute intervals to assess QT interval at the following timepoints:

- At baseline
- On Day 4, 4 hours (H4) after intake of fexinidazole, on Day 4 H23 and on Day 10 two to three hours after intake of fexinidazole.

Triplicate ECGs and a safety ECG will be collected for different purposes and will be analysed separately (see Section 6.3.2 ECG Recordings; p 46).

3. Study Design

This is an open-label, multicentre, Phase II/III study. The study will be a plug-in to the pivotal study, DNDiFEX004, and will be performed at the same sites.

4. Selection of Study Population

To be eligible for inclusion in the study, patients must fulfil all of the inclusion criteria and none of the exclusion criteria.

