6.5. Safety Assessments, Definitions and Reporting of Adverse Events

The safety and tolerability of treatment will be assessed through routine monitoring of adverse events (AEs). During the observation period, the study personnel will collect AEs on a daily basis.

The **observation period** will extend from the start of treatment (D1) to hospital discharge, which is planned at D18, but which may take place as early as D13, depending on the patient's status.

In addition, patients will be advised to return to the hospital/investigational centre at any time during the follow-up period if they experience any AEs, in order to undergo additional safety assessments.

Safety data will be reviewed at each meeting of the DSMB.

Safety endpoints will be classified as follows:

- Occurrence of any adverse events grade ≥ 3, including laboratory abnormalities, during the observation period. Adverse events will be graded according to the NCI CTCAE, Version 4.03 (38);
- Occurrence of any adverse events, including laboratory abnormalities, (all grades combined) during the observation period;

- Occurrence of any treatment-related adverse events, including laboratory abnormalities, (grade ≥ 3 and all grades combined) during the observation period and during the follow-up period;
- Occurrence of any serious adverse events, including laboratory abnormalities, during the observation period;
- Occurrence of any serious adverse events, including laboratory abnormalities, between the first intake of the IP and the end of the additional follow-up period (18 months).

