6.5.4. Adverse Event Collection Period

The periods for collection of AEs that occur in the context of the study are defined as follows:

- For all non-serious adverse events, the observation period extends from the first intake of fexinidazole on Day 1 until hospital discharge between D12 and D18
- For all serious adverse events, the observation period extends from enrolment of the patient in the study, i.e. after signature of the informed consent form, until the end of follow-up (18 months).

All AEs that occur during the AE collection period defined in the protocol must be recorded in the CRF, whether or not they are considered to be treatment related. In addition, all AEs that occur after the AE collection period, and that the Investigator considers as possibly related to the IP, must also be reported.

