Timepoint →	D-15 to D-1	D-4 to D-1	D1	D2	D3	D4	D5	D6	D7	D8	D9	D10	D11 (EOT)	D12	D13-D18	3 - 6 - 12 - 18
Triplicate ECG		x				x D4H4 D4H23						x D10H2-H3				
Administration of fexinidazole			х	х	х	х	х	х	х	х	х	х				
Adverse events (AEs) ⁷			х	х	х	х	x	х	х	х	x	x	х	х	x	
Serious adverse events (SAEs) (collection from signature of consent form to last study visit)		х	х	x	х	х	х	x	х	х	x	x	x	x	x	x
Collection of concomitant medication	х	х	х	х	х	х	х	х	х	х	х	х	х	x	х	
Blood sampling for DBS												x D10H3 D10H7:15	x D10H24	x D10H48		

⁷ In addition, any adverse event that occurs after the AE reporting period and considered as possibly treatment related by the Investigator must be reported.

Table 4 – Study Schedule

Final version of protocol	Version 1.0 – December 2013 Version 2.0 – March 2014					
Investigational Product available	January 2014					
First patient first visit	April 2014					
Duration of enrolment period	Approximately 24 months					
Duration of follow-up period	12 months (primary endpoint) – 18 months (follow-up)					
Last patient last visit	March 2017					
Final study report	December 2017					

Table 5 – Overall Study Organisation

Target Country	Democratic Republic of Congo (DRC)										
		Screened	Included								
Target Enrolment Rate	Total	150	125								
Number of sites	At least 8 sites										
Number of patients included per site	No limitation per site										
Participation of a	A Data and Safety Monitoring Board (DSMB) will be appointed to look										
DSMB	after safety issues (same DSMB as for DNDiFEX004										
Partners	 Swiss Tropical and Public Health Institute, Basel, Switzerland Monitoring Logistics (Swiss TPH/DNDi Kinshasa) Ministry of Health, Kinshasa, DRC Principal Investigator PNLTHA, Kinshasa, DRC Supervision of teams and investigational sites Coordination of supplies and active case detection teams MSF Technical support 										
Other means required	Logistical support Mobile teams for active case detection										
for study	Equipment and supplies for biochemical and haematological analyses										
	Telecommunication means and computer hardware/software

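### The treatment-related AE endpoint has two different windows, and 5.8.4 contradicts the AE sections on recording possibly related non-serious events in follow-up, so these may be under-captured

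*Protocol*

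**What the plan says.** **Endpoint window.** Protocol section 2.2.2 lists as a safety endpoint: "Occurrence of any treatment-related AEs (grade ≥ 3 and any grade) during the observation period". The protocol summary gives the same period. Section 6.5 lists the same endpoint with a longer one: "grade ≥ 3 and all grades combined) during the observation period and during the follow-up period". Section 6.5 also defines the observation period, which "will extend from the start of treatment (D1) to hospital discharge, which is planned at D18" but may end as early as D13.

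**Recording in follow-up.** Section 5.8.4 says: "Information on any SAEs that may occur during the follow-up period will be collected at unscheduled visits and recorded in the eCRF". The next sentence covers everything else: "Other medical events will be recorded only in the patient's medical file". It makes no exception for events thought to be related to the drug.

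**Reporting of late related events.** Section 6.5.4 ends the collection of non-serious AEs at hospital discharge, but then adds that "all AEs that occur after the AE collection period, and that the Investigator considers as possibly related to the IP, must also be reported". A footnote to Table 3 repeats this for "any adverse event that occurs after the AE reporting period and considered" possibly treatment related by the Investigator. In Table 3 itself, the AE row has no mark in the follow-up column, while the SAE row has one.

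**The concern.** A named safety endpoint should have one period. Here a reader of 2.2.2 would count related events up to discharge, and a reader of 6.5 would count them over a further 18 months or so. The two counts answer different questions, and a reported rate could not be interpreted without knowing which was meant.

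The recording conflict is the more serious of the two, because it acts at the sites. An analyst can choose a window later, but cannot analyse events that exist only in medical files. If some sites enter related non-serious events after discharge and others do not, the follow-up part of the endpoint is biased downwards by an unknown amount. A low count could then be taken as reassurance about delayed drug-related events in children.

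**Working it through.** No arithmetic applies: the protocol gives no expected rate of related AEs after discharge. The check is a comparison of the texts.

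**1. Window of the endpoint**

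| Place | Period for treatment-related AEs |
|---|---|
| Summary, secondary endpoints | Observation period |
| 2.2.2 | Observation period |
| 6.5 | Observation period and follow-up period |
| 9.9 | No period stated |

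The observation period ends at discharge, so the difference is the whole of follow-up, to 18 months after the end of treatment. Nothing in 9.9 settles which is intended.

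**2. Where a possibly related, non-serious event after discharge is recorded**

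| Place | Instruction |
|---|---|
| 5.8.4 | Medical file only |
| 6.5.1 | Identified AEs go in the AE section of the CRF |
| 6.5.4 | Must be reported; form not named |
| 6.5.5 | All AEs go in the CRF |
| 6.5.9 | Followed beyond the end of participation; resolution documented in the CRF |
| Table 3, AE row | No mark in the follow-up column |
| Table 3, footnote | Must be reported |

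A site cannot obey 5.8.4 as written and also obey 6.5.1, 6.5.5 and 6.5.9. Section 6.5.4 does not say that it overrides 5.8.4, and 5.8.4 does not refer to 6.5.4.

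**3. Whether such events can be expected to surface**

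- Section 6.5.3 has patients questioned about AEs at each follow-up visit.
- Section 6.5 tells patients to return if they have any AE during follow-up.
- Section 6.3.3 schedules haematology and biochemistry at week 9 and at 6 months, for patients who reach those visits after stated dates.
- Section 6.5.1 makes a laboratory abnormality above grade 1 that appears or worsens after the start of treatment an AE, unless it belongs to a clinical event already reported.

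The protocol therefore looks for these events and then gives opposite instructions on where to put them.

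**The case against.** The strongest reply is that the AE sections govern AE collection. Sections 6.5.1, 6.5.4, 6.5.5 and 6.5.9 and the Table 3 footnote all point towards reporting and CRF entry, against one sentence in a section on concomitant medication. That sentence speaks of medical events, not AEs, and follows one about unscheduled visits. It can be read as meaning intercurrent illness. The blank follow-up cells in the AE row are consistent with routine non-serious collection ending at discharge, with the footnote supplying the exception.

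Much of this stands. It means a recording route exists, and a reader who infers that the follow-up part of the endpoint would be empty goes further than the documents allow: that would require every site to set the AE sections aside. It does not remove the contradiction. The sentence in 5.8.4 is unqualified, and unscheduled visits are those at which patients return with AEs.

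Three other inferences are also unsupported:

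- **A confidence limit on zero observed follow-up events.** Section 6.5 defines one endpoint over both periods, to which in-hospital related events and related serious events in follow-up also contribute. A follow-up-only, non-serious rate is not an endpoint of this trial.
- **D18 as the latest end of the in-hospital window.** Section 6.1 provides for hospitalisation beyond D18.
- **A promised 95% confidence interval for the related subset.** Section 9.9 promises intervals for SAEs and AEs and does not name treatment-related AEs.

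**Conclusion.** Both contradictions are real. The treatment-related AE endpoint ends at discharge in 2.2.2 and the summary, but extends through follow-up in 6.5. Section 5.8.4 conflicts with 6.5.1, 6.5.4, 6.5.5, 6.5.9 and the Table 3 footnote on recording possibly related non-serious events after discharge. The consequence is possible under-capture of the follow-up part, to the extent that sites apply 5.8.4 literally. How many would do so, and how many events that would cost, cannot be derived from the protocol. Related serious events, in-hospital events and the primary efficacy analysis are not affected by the recording conflict. The point is worth correcting because one safety endpoint has two meanings, the possible loss of data occurs at the sites where a statistical analysis plan cannot repair it, and the correction is cheap.

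**What to change.** 1. State one window for the treatment-related AE endpoint in the summary, 2.2.2 and 6.5. Since 6.5.4 already requires possibly related events after discharge to be reported, a window that includes follow-up is consistent with the rest of the AE text.
2. In 9.9, report the in-hospital part and the follow-up part separately. Non-serious AEs are collected in full up to discharge and only if possibly related afterwards, so the two parts should not be merged without comment.
3. In 5.8.4, add an exception: possibly related AEs found at any scheduled or unscheduled follow-up visit are entered in the AE section of the CRF, as required by 6.5.4.
4. In Table 3, mark the follow-up column of the AE row for possibly related AEs.

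The cost is wording in the summary, 2.2.2, 5.8.4, 6.5, 9.9 and Table 3, plus CRF entry of the related events. Sites already ask about AEs at every follow-up visit, so no new visit or procedure is needed.

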5.9. Rescue Treatment

Patients who show no clinical response to treatment at the EOT visit, as well as patients with evidence of relapse, i.e. *T.b. gambiense* found in any bodily fluid, or of probable relapse at any time during follow-up will receive NECT, an alternative treatment for HAT, as per usual practice in the investigational centre.

The definition of probable relapse disclosed at the 6-month, 12-month or 18month follow-up visit is provided in Table 1.

Rescue treatment for HAT will not be recorded in the "Concomitant Treatment" section of the eCRF, but will be recorded as a comment on the "End of Study" page with the date of treatment start.

Table 1 – Clinical Management of Patients

Visit	Ideal timing of visit after end of treatment	Success	Probabale success	Probable failure	Proven failure
24 hours after EOT	Within 2 days	• Patient alive with no evidence of trypanosomes in any bodily fluid (54)			 Evidence of trypanosomes in any bodily fluid
3 months	3 months ± 1 week	 Patient alive with no evidence of trypanosomes in any bodily fluid (no lumbar puncture at 3 months unless Investigator suspects a relapse) 	 Any reason leading the Investigator to request an additional follow-up visit 	 Signs or symptoms suggestive of HAT and of treatment failure leading to use of rescue treatment 	 Evidence of trypanosomes in any bodily fluid
6 months	6 months ± 2 weeks	 Patient alive with no evidence of trypanosomes in any bodily fluid and CSF WBC ≤ 20/µL 	 CSF WBC between 20 and 50/µL and additional follow-up visit requested within 1 to 3 months Any reason leading the Investigator to request an additional follow-up visit 	 CSF WBC ≥ 50/µL (36) Neurological signs or symptoms leading to use of rescue treatment 	 Evidence of trypanosomes in any bodily fluid
12 months	12 months ± 4 weeks	 Patient alive with no evidence of trypanosomes in any bodily fluid and CSF WBC ≤ 20/µL 	 CSF WBC > 20/µL and clinically non-significant increase as compared to previous value(s) CSF WBC > 20/µL and < 50/µL and reduced as compared to previous value(s) Any reason leading the Investigator to request an additional follow-up visit within 1 to 3 months 	 CSF WBC ≥ 50/µL Signs or symptoms suggestive of HAT and of treatment failure leading to use of rescue treatment 	 Evidence of trypanosomes in any bodily fluid
18 months	18 months ± 4 weeks	 Patient alive with no evidence of trypanosomes in any bodily fluid and CSF WBC ≤ 20/µL Patient with no signs of HAT who refuses to undergo lumbar puncture and who, in the opinion of the Investigator, does not require rescue treatment or an additional follow-up visit 	Any reason leading the Investigator to request an additional follow-up visit within 1 to 3 months	 CSF WBC > 20/µL Signs or symptoms suggestive of HAT and of treatment failure leading to use of rescue treatment 	 Evidence of trypanosomes in any bodily fluid

An uncertain outcome may be a discrepancy between the clinical picture and the laboratory findings, or any situation that leads the Investigator and the study team to consider that an additional follow-up visit is required to decide whether or not to provide rescue treatment.

6. Schedule of Study Procedures and Assessments

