2.2. Study Endpoints

2.2.1. Primary Efficacy Endpoint

The primary efficacy endpoint is the outcome, i.e. success or failure, observed at the test-of-cure (TOC) visit, 12 months after the end of treatment (EOT).

Success at 12 months, adapted from WHO criteria (54), is defined as:

- Patient cured, i.e.:
 - o patient alive,
 - AND no evidence of trypanosomes in any bodily fluid,
 - o AND CSF WBC ≤ 20/μL.

A patient with no evidence of trypanosomes in any bodily fluid, but with CSF WBC > $20/\mu$ L, or who, in the opinion of the Investigator, requires rescue treatment will be considered as a probable relapse.

Patients lost to follow-up and retrieved after 12 months or patients who refuse to undergo lumbar puncture at 12 months will be considered as patients probably cured, i.e. successes, if they have no clinical signs or symptoms suggestive of HAT or if their symptoms can be clearly attributed to another aetiology, provided that the outcome was favourable at the last available assessment of HAT (6-month visit or subsequent unscheduled visit). If a patient is not assessed, i.e. has no lumbar puncture, at 12 months, but has a lumbar puncture or physical examination subsequently or at 18 months, the outcome at the latter visit will prevail over that at 12 months.

Patients who die due to any cause, patients lost to follow-up and not retrieved, and patients who refuse to undergo lumbar puncture at 12 months and whose clinical outcome had previously been assessed as unfavourable, i.e. probable relapse, will be considered as failures.

The prinicipal visit for assessment of the efficacy endpoint, i.e. success or failure, was set at 12 months after the EOT because the relapse rate between 12 and 18 months is very low and highly consistent across the various treatments administered to patients with stage-2 HAT (historical data). The success rate for melarsoprol was 74.84% at 12 months and 73.71% at 18 months, i.e. a relapse rate of 1.1% (n=3477), (61). The success rate for effornithine was 90.3% at 12 months and 89.1% at 18 months, i.e. a relapse rate of 1.2% (n=743), (61). The relapse rate for NECT was 1.4% (n=143) between 12 and 18 months after the EOT (43). Consequently, the overall relapse rate between 12 and 18 months after the EOT is around 1.2% for patients with stage-2 HAT, regardless of the treatment. The consistency of the findings suggests that the success rate at 12 months is predictive of the success rate at 18 months.

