6.4.4. At Unscheduled Visits

If a relapse is suspected on the basis of physical examination findings or CSF WBC count, at any visit, the patient must attend a return visit within 1 to 3 months, at the discretion of the Investigator.

The patient must also return to the investigational centre if s/he does not feel well, even if there is no apparent relationship with treatment and/or HAT.

The following assessments will be performed:

- Physical examination, HAT symptoms since the last visit, neurological assessment, including signs and symptoms of HAT;
- Investigation of any concomitant condition that may have led to the visit;
- Testing for *T.b. gambiense* in blood and lymph, if indicated;
- CSF sampling (Fuchs-Rosenthal/Fast Read 102[®] counting chamber, MSC with INRB kits): only if symptoms suggesting disease progression are present;
- Additional safety assessments such as ECG, haematology, biochemistry or urine tests may be performed at the discretion of the Investigator.

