9.2. Handling of Missing Data and Patients Lost to Follow-up

The primary endpoint is the outcome, i.e. success or failure, of treatment at the 12-month visit. If the outcome at the 12-month visit is missing, the **primary method of imputation** will consist in imputing a probable success (considered as a success) to patients who attended the visit but who refused the lumbar puncture planned for the visit, who showed no signs or symptoms of HAT at 12 months, who did not subsequently report any symptoms of relapse and for whom the outcome was considered as favourable at the last available assessment (42). If these criteria are not fulfilled, the patients will be considered as treatment failures. The outcome for patients lost to follow-up from the 12-month visit onwards will also be considered as a failure.

Two additional methods for imputing missing data will be used.

The **second method** will consist in imputing failure if there is no lumbar puncture at 12 months or later.

In the **third method**, missing data will not be imputed. All patients for whom an assessment is available at a given timepoint will be included in the estimate of the success rate at that timepoint. If a value is missing at an intermediate visit,

followed by a success or a failure at one of the subsequent visits, the status at the subsequent visit will prevail over the status at the intermediate visit. In the Kaplan-Meier approach, the observation is censured at the first missing outcome, provided that all subsequent outcomes are also missing.

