9.8. Efficacy Analysis

9.8.1. Primary Efficacy Analysis

Primary Efficacy Endpoint

The primary efficacy endpoint is the. success or failure, at 12 months after the final treatment intake. The patient's treatment will be a success if there is no evidence of trypanosomes in any bodily fluid, and the WBC count in the CSF is $\leq 20/\mu$ L. Patients with no parasitological evidence of relapse, but with a CSF WBC count > 20/µL or who, in the opinion of the Investigator, require rescue treatment, will be considered to be probable relapses and therefore as failures. Death due to any cause or use of rescue medication will be considered as a relapse, i.e. a failure. A patient who attends the follow-up visit at 12 months or later and who

refuses to undergo lumbar puncture, but who has no signs or symptoms of HAT and for whom the outcome was assessed as favourable at the last assessment will be considered as a probable cure, i.e. a success, unless signs of relapse are detected on any assessment up to 18 months.

Primary Analysis

The primary analysis will be performed on the ITT population.

The primary endpoint is the success or failure of treatment, as defined above.

The primary analysis of success or failure will be performed at 12 months of follow-up.

The primary test is an exact test derived from the exact confidence interval (CI) of the success rate at 12 months.

Two sets of statistical hypotheses will be tested simultaneously:

 H_{0A} : the true success rate is equal to or less than 80%, which is considered to be unacceptable.

H_{1A}: the true success rate is greater than 80%.

 H_{0B} : the true success rate is equal to or greater than 92%, which is the target or expected success rate for fexinidazole.

H_{1B}: the true success rate is less than 92%.

If H_{0A} is rejected, then the success rate is significantly greater than 80% and the estimated rate is consistent with a rate of 92%. In this case, H_{0B} is automatically accepted, but not necessarily true.

If H_{0B} is rejected, then the success rate is significantly less than the target of 92%, and the estimated rate is consistent with the unacceptable rate of 80%. In this case, H_{0A} is automatically accepted, but not necessarily true.

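### At 12 months a CSF WBC above 20/µL is a failure in sections 2.2.1 and 9.8.1, but some such counts are a probable success in Table 1, which section 5.9 names as the source of the relapse definition

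*Protocol*

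**What the plan says.** **Endpoint text.** Section 2.2.1 requires CSF WBC ≤ 20/µL for success at 12 months. A child without trypanosomes but with a count above 20/µL, or who "in the opinion of the Investigator, requires rescue treatment will be considered as a probable relapse". Section 9.8.1 repeats the rule and says that these children "will be considered to be probable relapses and therefore as failures". Neither section makes an exception for the trend or the size of the change. Section 9.8.1 also counts any use of rescue medication as a failure.

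**Rescue text.** Section 5.9 gives rescue treatment to patients with relapse or probable relapse and then says: "The definition of probable relapse disclosed at the 6-month, 12-month or 18month follow-up visit is provided in Table 1". Table 1 is titled as clinical management, and its columns are success, probable success, probable failure and proven failure. In the 12-month row, probable success includes:

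- a count above 20/µL with a "clinically non-significant increase as compared to previous value(s", with no upper limit;
- a count above 20 and below 50/µL that is "reduced as compared to previous value(s".

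On the count alone, probable failure in that row starts at 50/µL. In the 18-month row, a count above 20/µL is by itself a probable failure.

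**The concern.** Probable relapse is the term by which 2.2.1 and 9.8.1 assign failure, and 5.9 says that its definition is in Table 1. Table 1 has no column of that name; the nearest is probable failure. At 12 months, the primary timepoint, that column does not cover all the counts that the endpoint sections call probable relapse. A child at 30/µL and falling is a failure in 9.8.1 and a probable success in Table 1.

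Two things are at stake. One is consistent classification of the objective laboratory part of the primary endpoint. One Table 1 criterion turns on an undefined judgement of clinical non-significance, made in an open-label trial. The other is which children come under the rescue rule, since 5.9 ties rescue to probable relapse.

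**Working it through.** **1. The passages side by side, for a parasite-free child at 12 months with no other reason for rescue**

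| CSF WBC at 12 months | 2.2.1 and 9.8.1 | Table 1, 12-month row |
|---|---|---|
| ≤ 20/µL | success | success |
| > 20 and < 50/µL, reduced | probable relapse, failure | probable success |
| > 20 and < 50/µL, increase judged non-significant | probable relapse, failure | probable success |
| ≥ 50/µL, increase judged non-significant | probable relapse, failure | probable success and probable failure |
| ≥ 50/µL, otherwise | probable relapse, failure | probable failure |

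Rows 2 and 3 are the conflict between sections. Row 4 is an overlap within Table 1. It needs a rise that ends at or above 50/µL and is judged non-significant, for example from 48 to 52/µL.

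**2. The plan's own figures**

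Inputs from 9.1 and 9.8.1: n = 125, unacceptable rate 80%, target 92%, one-sided alpha 0.025, success at 109 or more. With X ~ Bin(125, p):

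- P(X ≥ 109 | 0.92) = 0.978; the protocol states 97.5% and says that the power achieved is slightly higher than desired.
- P(X ≤ 108 | 0.80) = 0.976; the protocol states 97.5%.
- P(X ≥ 109 | 0.80) = 0.0243, below 0.025 as the protocol says.
- Exact 95% CI for 109/125: 80.05% to 92.5% (study success). For 108/125: 79.1% to 91.9% (study failure).

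The sample size and threshold are correct and not in dispute. At the threshold, one child classified differently changes the result.

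**3. Size of the conflict**

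The documents do not say how many children would fall in the disputed rows. Assumption: k disputed children (1, 3 or 5), with the other 125 − k succeeding independently at rate p (90%, 92% or 94%).

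- Counted as successes: P(Y ≥ 109 − k), Y ~ Bin(125 − k, p)
- Counted as failures: P(Y ≥ 109), Y ~ Bin(125 − k, p)

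Probability of study success, counted as successes versus as failures:

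| p in the other children | k = 1 | k = 3 | k = 5 |
|---|---|---|---|
| 90% | 88.7% vs 82.5% | 89.9% vs 66.5% | 91.0% vs 45.6% |
| 92% | 98.0% vs 96.1% | 98.2% vs 89.1% | 98.5% vs 74.8% |
| 94% | 99.9% vs 99.7% | 99.9% vs 98.5% | 99.9% vs 94.3% |

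The gap is large when the disputed children are several and the rate in the others is near the threshold. For k = 5 and p = 90%, the expected rate is (120 × 0.90)/125 = 86.4% if they are failures and (108 + 5)/125 = 90.4% if they are successes, on either side of the 87.2% threshold. With one child and p = 94% the gap is negligible.

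**The case against.** The strongest answer is that the primary endpoint is already fixed. It is defined in 2.2.1 and again in 9.8.1, and 9.8.1 ties the primary analysis to its own definition. Table 1 stands under rescue treatment, carries a clinical-management title, and is followed by a note about extra visits to decide on rescue. An analyst who follows 9.8.1 obtains one success rate. This stands, and it limits the point to a conflict between sections. It does not remove the point, because 5.9 expressly places the definition of probable relapse in Table 1 and nothing says which text prevails. Section 10.2 has a committee assess the consistency of the success and failure rules before database lock, but gives it no order of precedence.

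A reader might infer more than the documents support:

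- **That section 9.2 scores these children as successes.** Its phrase "imputing a probable success (considered as a success" concerns a missing 12-month outcome after a refused lumbar puncture, not a measured count.
- **That a rise from 55 to 60/µL shows the overlap in Table 1.** If 55/µL was the 6-month value, the 6-month row already makes it a probable failure. The overlap needs a rise across 50/µL or an intervening unscheduled value.
- **That section 6.4.4 is a third conflicting rule.** It says that on suspected relapse "the patient must attend a return visit within 1 to 3 months, at the discretion of the Investigator". No contradiction with the endpoint text is shown.
- **That rescue adds failures to the primary count.** Under 9.8.1 a child above 20/µL at 12 months is a failure with or without rescue. Rescue given for that count could change only a tally that follows Table 1.
- **That the one-patient margin is special to this defect.** Any count threshold has one.

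**Conclusion.** The inconsistency is real and should be fixed. Section 5.9 names a source for the relapse definition that contradicts the endpoint sections at the primary timepoint, and Table 1 overlaps itself at 50/µL and above. The documents do not support the stronger conclusion that the primary endpoint is undefined or that the planned analysis yields two success rates: 9.8.1 read alone is explicit.

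The size is uncertain because the number of disputed children is not given. Over the assumed range of 1 to 5 children and 90% to 94% success in the others, the consequence runs from negligible (99.9% versus 99.7%) through 98% versus 89% (3 children, 92%) to 91% versus 46% (5 children, 90%). At the target rate of 92% in the other children, the gap is about 2 to 24 percentage points.

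**What to change.** 1. State in 9.8.1, and by cross-reference in 5.9, that 9.8.1 governs the primary and other 12-month analyses: CSF WBC above 20/µL is a failure whatever the trend, and Table 1 does not define the endpoint.
2. Add one sensitivity analysis that counts children in the 12-month probable success column of Table 1 as successes.
3. Have the sponsor reconcile 5.9 and Table 1 with 2.2.1 and 9.8.1 on the definition of probable relapse and the trigger for rescue, including the overlap at 50/µL and above. Which clinical threshold is right is for the sponsor; this review takes no position.

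The cost is amendment and analysis-plan wording plus one analysis of data already collected. The sample size and decision threshold do not change.
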